6. OBJECTIVES

6.1. Primary Objectives

The primary objectives of this study are to (a) determine the feasibility of giving patients and providers monthly feedback about TFV-DP levels and (b) examine patient and provider behaviors in response to receiving this information, specifically patient medication adherence as measured with Wisepill, and clinical management of patients.

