8.1 Inclusion/Exclusion Criteria

8.1.1. Patient Participant Inclusion Criteria

Individuals who meet all of the following criteria are eligible for inclusion in the study:

- 18 years of age or older
- HIV-positive
- Initiated ARV's containing tenofovir 4 or more months ago

- Speaks English or Xhosa
- Willing to attend 5 study visits approximately one month apart
- Willing to allow the study team to contact his/her HIV care provider about his/her monthly TFV-DP drug level
- Willing to use Wisepill to dispense ARVs for 4 months
- Willing to receive SMS and/or phone call reminders to charge the Wisepill
- Willing to allow the study team access to their medical chart/clinic folder

Participants will be recruited without regard to gender or race/ethnicity. However, based on clinic profiles, we expect the majority (about 70%) to be women and over 90% to be Black African, with the remainder, if any, of mixed race.

To generate a study sample that closely represents the clinic population, participants will be recruited regardless of VL. Based on clinic profiles, we expect the majority of participants (about 80%) to be virally suppressed based on the last standard of care (SoC) VL with the remainder being unsuppressed. The South African National Health Laboratory Service (N HLS), which assays the VL, currently uses a cut-off of less than 50 copies/mL to denote undetectable VL.

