12. STATISTICAL CONSIDERATIONS

12.1. Overview and General Design Issues

For Aim 2, we will explore whether providing adherence feedback to patients and providers results in changes to patient adherence behavior (as measured by TFV-DP levels, VL, Wisepill use patterns, and self-report) and/or provider behavior with respect to patient management (e.g., requests for additional laboratory tests, calling patient back for an additional appointment, referring patient to an adherence counselor, referring patient to the 'risk of treatment failure clinic'). Below we describe the analytical plan to assess change in patient adherence behavior using Wisepill openings as an example.

This 5-month pilot with a small sample size, will provide preliminary estimates that can be used to inform future power calculations and the design of a larger trial (e.g., estimates of effect size, interclass correlation [ICC] for within individual and within provider/clinic correlation). Using Aim 1 data on self-reported adherence, which includes about 3,000 observations, the mean adherence is 81.96% with a standard deviation of 11.42%. The current plan to recruit 60 subjects and collect their monthly adherence data over the subsequent 4-month period will result in 180 change scores (90 per group) for the Aim 2 analysis. Using the estimated standard deviation from our existing data and assuming the ICC between successive change scores is no greater than 0.20, we will be able to detect a 5.59 percentage point difference in ART adherence between the intervention and control group with 80% power. Assume the mean adherence is about 80% for the control group (very close to what we observed from our observational study in Aim 1), if in truth, the mean adherence is 85.59% (which we optimistically believe is achievable), we have 80% probability to declare the difference of adherence between intervention and control is statistically significant. Therefore, we believe that the data we will collect from 60 participants over the 4-months of follow up will provide adequate power to achieve the study goal.

To generate preliminary estimates of the effect of giving feedback on adherence behavior, we will compare change in average percentage of Wisepill openings (for example) from one month to the next between Feedback and No Feedback (Control) participants.

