Because feedback begins at the first return visit at Month 1 after baseline, each Feedback Group participant will provide up to three change score outcomes (for month $i-1$ to month i for $i=2,3,4$). We will compare these to the corresponding change scores in the Control Group in a generalized linear model (GLM) using generalized estimating equations (GEE) to account for within-subject correlation (ICC) among their three change-scores. The analysis model will include a constant term and the group indicator.

With the limited pilot sample size of 60, we will be able to detect moderately large effects on average improvement in adherence. For example, if the ICC between successive change scores is no greater than 0.20, then the detectable standardized mean difference will be $2.8 * [(2/30) * (1 + 0.2 * (3-1))]^{1/2} = 0.86$, a "large" effect.

Given that this is a pilot study, our ability to explore the role of the moderating variables on adherence-related behavior will be limited. However, looking at the monthly change-scores can reveal important features on which to focus. Moreover, the larger Aim 1 sample (N=250) will provide key data on individual and structural factors affecting adherence, retention, and preferences for sample collection and feedback that we will utilize in multivariable analyses as predictors of DBS TFV-DP levels and Wisepill use patterns. We will also examine these factors as potential effect modifiers in Aim 1 analyses.

For providers we will examine changes in clinical management patterns, for example requests for additional tests or adherence counselling sessions usually only triggered by a raised VL.

Similar to Aim 1, the Baseline and Visit 4 (last visit) Quantitative Assessments will cover a large array of participant information and behaviors that could be potential confounders. To examine how potential confounding factors can influence our statistical analysis, we will first identify a list of variables that is possible be candidates for potential confounding factors and then test whether any of those variables is associated with our outcome (i.e., adherence) and exposure (i.e., the intervention) in our sample. If found, we will include them in the primary analysis model to obtain the adjusted intervention effect. While the official primary analysis will be the one without covariate adjustment, the adjusted analysis will help to interpret the findings from primary analysis.

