12.4. Randomization/Blinding Procedures/Unblinding Procedures

Participants in the pilot study will be randomized 1:1 to either Feedback Group (N=30) or No Feedback (Control) Group (N=30) by study staff using a randomization list generated by the study Biostatistician ([name]). The study will not be blinded.

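### Section 12.1 claims adequate power for the whole study goal from a calculation on patient adherence only; no power or precision is given for provider management

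*Combined protocol and SAP*

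**What the plan says.** Objective (b) in section 6.1 has two measured parts: "specifically patient medication adherence as measured with Wisepill, and clinical management of patients". Section 12.1 opens the same way, setting out to explore patient adherence "and/or provider behavior with respect to patient management".

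The power calculation in 12.1 then uses one patient measure: "Using Aim 1 data on self-reported adherence, which includes about 3,000 observations", for which "the mean adherence is 81.96% with a standard deviation of 11.42" percent. With 180 change scores and an ICC of at most 0.20, it gives 80% power for a difference of 5.59 percentage points. From this it infers that "the data we will collect from 60 participants over the 4-months of follow up will provide adequate power to achieve the study goal".

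Later in 12.1 a second detectable effect appears, a standardized difference of 0.86. It too concerns adherence. The provider side gets one sentence, which ends by naming an elevated viral load as the usual trigger: "For providers we will examine changes in clinical management patterns, for example requests for additional tests or adherence counselling sessions usually only triggered by a". Section 12.4 fixes the arm sizes: "randomized 1:1 to either Feedback Group (N=30) or No Feedback (Control) Group (N=30").

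**The concern.** The conclusion is wider than its basis. The adherence calculation rests on a continuous score with three changes per participant and a known SD. None of those inputs carries over to actions abstracted from clinic charts, so the adequacy claim is unsupported for the provider half of objective (b).

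The consequence lies in interpretation. Section 5.2 presents this as the first study of how providers use drug-level feedback, and 12.1 says its estimates will inform a larger trial. If a provider comparison is reported and is not significant, a reader told that the study was adequately powered for its goal may conclude that providers do not act on the results. The data might be too few to say so.

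**Working it through.** **1. The plan's adherence figure (section 12.1).** Inputs: 30 per arm, 3 change scores each, ICC 0.20, SD 11.42. Two-sided 5% is not stated; it is inferred from the plan's multiplier of 2.8 (1.96 + 0.84).

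- Effective n per arm = 30 × 3 / (1 + 0.2 × 2) = 64.3.
- Standard error = 11.42 × √(2/64.3) = 2.01.
- Power at 5.59 = Φ(5.59/2.01 − 1.96), about 79%. The detectable difference at 80% power is 5.64.

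The 80% claim reproduces for adherence under those inputs.

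**2. The second adherence figure (also 12.1).** The plan computes 2.8 × √[(2/30) × (1 + 0.2 × 2)] = 0.86 SD. At SD 11.42 that is 9.8 points. The earlier figure is 5.59/11.42 = 0.49 SD. The design is the same; the second formula does not divide by the three scores per participant. With it, effective n per arm is 30/1.4 = 21.4, and power at 5.59 points is about 36%.

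**3. The provider comparison.** The plan gives no inputs, so the following are assumptions: a binary outcome (at least one provider action per participant), 30 v 30, two-sided 5%, and control rates p0 of 5%, 10% and 20%. Power is the sum, over all pairs of counts (a, b), of Bin(a; 30, p0) × Bin(b; 30, p1) where the test rejects. The tests are the pooled z test (|z| ≥ 1.96) and Fisher's exact test (p ≤ 0.05).

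Smallest difference with at least 80% power, in percentage points:

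| Control rate | Pooled z | Fisher |
|---|---|---|
| 5% | 26 | 31 |
| 10% | 31 | 34 |
| 20% | 35 | 38 |

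**4. What that requires of feedback.** Let f be the share of Feedback participants with an actionable drug level, and suppose providers act on every one. Then p1 = p0 + f(1 − p0). For example, p0 = 10% and f = 30% give p1 = 37%. Power, z / Fisher:

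| f | p0 = 5% | p0 = 10% | p0 = 20% |
|---|---|---|---|
| 20% | 60% / 40% | 43% / 31% | 28% / 20% |
| 30% | 85% / 75% | 72% / 61% | 52% / 41% |
| 40% | 97% / 93% | 91% / 85% | 75% / 66% |
| 50% | >99% / 99% | 98% / 96% | 91% / 85% |

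If providers act on only some actionable results, f is replaced by f times the proportion acted on, and power falls accordingly. No allowance is made for the dropout of up to 10% in section 12.6, or for participants sharing a provider or clinic.

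**5. Precision.** The 95% half-width is 1.96 × √[p0(1 − p0)/30 + p1(1 − p1)/30]. For 10% v 30% it is 19.6 points; for 20% v 40% it is 22.6 points.

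**The case against.** The best defence is context. The sentence follows directly from an adherence calculation, in a passage introduced as the plan for patient adherence. The only stated hypothesis (5.3, 12.3) is better patient adherence. Section 12.1 also calls the sample small and its results preliminary. No provider test is specified, and chart-recorded actions are not listed in the primary endpoint (12.2.1). A pilot need not be powered for provider behaviour, and the focus groups in 9.6 address provider response directly. All of this stands, and it makes the point one of scope rather than of wrong arithmetic. It does not remove the point: the claim refers to the study's goal without limit, and the plan puts provider management inside that goal.

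A reader might go further and infer that the provider comparison is underpowered at any plausible rate. One route is section 8.1.1, where "we expect the majority of participants (about 80%) to be virally suppressed": if actions follow raised viral load, only about 20% of participants would be actionable. The documents do not support that step. Providers receive TFV-DP results, not the study viral loads (9.3, 9.9.1.3). Section 5.1.3 argues that drug levels flag risk in suppressed patients as well. Table 1 schedules feedback on three occasions, so the share ever flagged can exceed the share flagged at any one visit. No action threshold is stated. At 40-50% actionable, all acted on, power is 75% to over 99% by z test and 66-99% by Fisher. A repeated or count outcome from the chart reviews in 9.5 is also possible and would change the figures.

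**Conclusion.** The adequacy statement is supported by a calculation for patient adherence and by nothing for provider management, which is part of the same objective. Under the assumed binary outcome, the provider comparison needs a difference of about 26-35 points (z) or 31-38 points (Fisher) for 80% power, at control rates of 5-20%. The documents cannot settle whether that is within reach. With every actionable result acted on, z-test power is about 28-60%, 52-85%, 75-97% and over 90% at actionable shares of 20%, 30%, 40% and 50%. The finding is therefore that adequacy is unsupported, not that the provider comparison is shown to be inadequate. Nor should the claim be treated as secure for adherence, because 12.1 gives two incompatible detectable effects, 0.49 SD and 0.86 SD, for one design.

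**What to change.** In section 12.1:

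- Limit the concluding sentence to the patient-adherence comparison and remove its reference to the goal of the study.
- Reconcile the 5.59-point figure (0.49 SD) with the 0.86 SD figure (9.8 points) before describing even the adherence comparison as adequately powered.
- State that the provider comparison is for estimation, reported as an arm difference with a 95% confidence interval. An expected half-width of about 20-23 points can be quoted if it is labelled as assuming rates of 10% v 30% or 20% v 40%.
- State that a non-significant provider difference will not be read as evidence of no provider response.

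This changes wording only and needs no further participants or data. The cost is a narrower and less favourable power statement.

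### Section 12.1 gives two detectable effects for one design (5.59 points, or 0.49 SD, and 0.86 SD), and its 80% power for a gap in level does not carry over to the change-score primary model

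*Combined protocol and SAP*

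**What the plan says.** All of this is in section 12.1 of the combined protocol and SAP unless noted.

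- **Inputs.** From about 3,000 Aim 1 self-report observations, "the mean adherence is 81.96% with a standard deviation of 11.42" percent. There are 60 participants, three change scores each (90 per arm), and an ICC between successive change scores of at most 0.20.
- **First detectable effect.** "we will be able to detect a 5.59 percentage point difference in ART adherence between the intervention and control group with 80% power". The illustration is a control mean of 80%: "if in truth, the mean adherence is 85.59% (which we optimistically believe is achievable), we have 80% probability to declare the difference". The section concludes that the data "will provide adequate power to achieve the study goal".
- **Primary model.** Feedback starts at the Month 1 visit, so "each Feedback Group participant will provide up to three change score outcomes": Months 1 to 2, 2 to 3 and 3 to 4. "The analysis model will include a constant term and the group indicator". The analysis without covariates is the official primary one. Wisepill openings serve as the worked example.
- **Second detectable effect.** For the same 60 participants and the same ICC, "then the detectable standardized mean difference will be" 2.8 × [(2/30) × (1 + 0.2 × (3 − 1))]^½ = 0.86, which the plan calls large.
- **Dropout.** Section 12.6 expects no more than 10%. Neither calculation allows for it.

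**The concern.** There are two faults.

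First, the same arms, number of scores and ICC lead to two detectable effects that differ 1.75-fold when put on the plan's one stated SD. A reader cannot tell which describes the trial.

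Second, the power statement and the primary model are on different scales. The power statement concerns a difference in average adherence level and uses an SD of levels. The model's group coefficient is a difference in average change per month. A level gap that opens after feedback and then holds appears once in the change scores and is averaged over three of them.

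The section says the pilot's estimates will feed the power calculation for a larger trial. If a per-month coefficient is read as a level difference, or the reverse, the effect size carried forward is wrong by a factor of three.

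**Working it through.** **Inputs from the plan:** n = 30 per arm, m = 3 change scores per person, ICC = 0.20, SD = 11.42 points. The multiplier 2.8 = 1.96 + 0.84 implies two-sided 5% and 80% power.

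**1. Reproduce 5.59 points.**
- SE = 11.42 × √[(2/90) × 1.4] = 2.014.
- Detectable difference = 2.8 × 2.014 = 5.64 points. Power for 5.59 is 79%. The figure reproduces within rounding.
- 5.59 / 11.42 = 0.49 SD.

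**2. Reproduce 0.86.**
- 2.8 × √[(2/30) × 1.4] = 0.855. The printed formula reproduces.
- It carries the inflation for correlated scores (1.4) but not the division by three. With 2/90 it is 2.8 × √[(2/90) × 1.4] = 0.494 SD.
- The two formulas differ by √3 = 1.73. In points at SD 11.42, 0.855 SD is 9.8, and 9.77 / 5.59 = 1.75.

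**3. Dropout in the plan's first calculation** (27 per arm, 81 scores per arm, dropouts contributing nothing): SE = 11.42 × √[(2/81) × 1.4] = 2.123. Power for 5.59 is 75%, and the detectable difference is 5.9 points.

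**4. What the primary model estimates.** Write M1 to M4 for a person's monthly values. The three changes telescope: (M2 − M1) + (M3 − M2) + (M4 − M3) = M4 − M1. With complete data and an independence or exchangeable working correlation, the group coefficient is therefore the arm difference in mean (M4 − M1)/3. GEE fits with both working correlations agreed with this to rounding error.
- A 5.59-point gap at Month 4, with none at Month 1, is 5.59 / 3 = 1.86 points per month.
- A coefficient of 5.59 points per month would mean 3 × 5.59 = 16.8 points by Month 4.

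The calculation in step 1 does work for levels, but only if 0.20 is the correlation between a person's monthly levels. The plan gives 0.20 for change scores.

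**5. Power of the primary model for a 5.59-point Month 4 gap.** SE of the gap = SD(M4 − M1) × √(2/n). For 80% power:
- n = 30: SD(M4 − M1) ≤ 5.59 / (2.8 × √(2/30)) = 7.7 points.
- n = 27: SD(M4 − M1) ≤ 5.59 / (2.8 × √(2/27)) = 7.3 points.

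The documents do not give this SD. As an assumption, take SD 11.42 at both months and Month 1 to Month 4 correlation r, so SD(M4 − M1) = 11.42 × √[2(1 − r)]:

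| r (assumed) | SD(M4 − M1) | Power, n = 30 | Power, n = 27 | Detectable Month 4 gap, n = 30 | Per month, n = 30 |
|---|---|---|---|---|---|
| 0.3 | 13.5 | 36% | 33% | 9.8 | 3.3 |
| 0.5 | 11.4 | 47% | 44% | 8.3 | 2.8 |
| 0.7 | 8.8 | 69% | 64% | 6.4 | 2.1 |
| 0.8 | 7.2 | 85% | 81% | 5.2 | 1.7 |

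Power reaches 80% at r of about 0.77 (n = 30) or 0.79 (n = 27). If the correlation decays month by month as AR(1), 0.77 three months apart needs 0.771^(1/3) = 0.92 between adjacent months.

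**The case against.** **The 0.86 has no stated unit.** It could be in units of a change-score SD, and at about 6.5 points (5.59 / 0.855) the two figures would coincide. That is possible in principle, so the 9.8 points is a conversion at SD 11.42, not a figure the plan prints. But the plan gives no such SD, and it takes the SD behind 5.59 from Aim 1. The missing division by three stands whatever the unit.

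**Power may be adequate.** At a correlation of 0.8 it is 85%. This is right, and it limits the point: the claim is unsupported, not shown to be false.

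**The telescoping result has conditions.** The plan names no working correlation and allows fewer than three scores. With weights matched to equally correlated levels (0.3, 0.4, 0.3), power at r = 0.3, 0.5 and 0.7 becomes 33%, 44% and 64% for a gain held from Month 2, or 39%, 52% and 73% for a linear build. The figures move modestly and the conclusion does not change.

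**The 27-per-arm figures are pessimistic.** Section 12.7.1.2 lets dropouts return, and GEE uses partial data. They are lower bounds.

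**This is a pilot with Wisepill as an example.** That lowers the consequence: feasibility is one of the two primary objectives, and no decision rule in the plan rests on power. But the plan itself claims 80% power and adequacy, and section 6.1 names Wisepill as the measure of patient adherence.

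**Conclusion.** The point holds, and section 12.1 should be corrected. The two detectable effects conflict because the 0.86 formula leaves out the division by three; on the plan's inputs it should read 0.49 SD. This follows from the plan's own numbers.

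The 80% power for 80% against 85.59% belongs to a comparison of levels and does not transfer to the change-score model, where the same Month 4 gap is a coefficient of 1.86 points per month. That step is algebra, given complete data and an independence or exchangeable working correlation. The model's actual power is unknown. It is 80% or more only if the SD of the Month 1 to Month 4 change is at most 7.7 points. The range of 36% to 85% rests on assumed correlations of 0.3 to 0.8 and on a self-report SD standing in for Wisepill.

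**What to change.** Make these three changes together. Correcting the formula alone and reusing 11.42 would give 5.64 points per month, or 3 × 5.64 = 16.9 points by Month 4.

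1. Replace 2/30 with 2/90 in the 0.86 formula, or otherwise reconcile it with 5.59 points.
2. Remove the 80% against 85.59% sentence and the conclusion of adequate power as applied to the change-score model. State instead the detectable change per month, X = 2.8 × √(2/n) × SD(M4 − M1) / 3, with the matching Month 4 gap 3X, for n = 30 and n = 27.
3. State the change-score SD and correlation and their source. The SD of a three-month change can be estimated from the Aim 1 self-report data. Note the limits of that source: section 5.1.4 describes a cohort virally suppressed at enrollment, whereas section 8.1.1 here admits patients at any viral load and the example outcome is Wisepill.

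The cost is rewording and one calculation from data already held. Sample size, visits and analysis model do not change.

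If the team wants the average level after feedback, a GEE of Months 2 to 4 on group, month and the Month 1 value is an option. It changes the estimand and is not always stronger. With equally correlated months at 0.7 and 30 per arm, its power against the change-score model is 93% to 69% for a gain held from Month 2, but 62% to 69% for a linear build.

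### Section 12.1 mixes monthly changes with adherence levels, so its 80% power for 5.59 points is unsupported for the planned GEE, and it conflicts with the 0.86 SD in the same section

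*Combined protocol and SAP*

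**What the plan says.** All of the relevant text is in Section 12.1.

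- **Source of the SD.** "Using Aim 1 data on self-reported adherence, which includes about 3,000 observations, the mean adherence is 81.96% with a standard deviation of 11.42" percent. This is the spread of adherence levels.
- **Detectable difference.** The second paragraph counts 180 change scores, 90 per group, and then says: "assuming the ICC between successive change scores is no greater than 0.20, we will be able to detect a 5.59 percentage point difference", with 80% power.
- **Illustration.** With a control mean of about 80%, "if in truth, the mean adherence is 85.59% (which we optimistically believe is achievable), we have 80% probability to declare" a significant difference. No month is attached to the 85.59%. The paragraph concludes that the data "will provide adequate power to achieve the study goal".
- **Planned model.** Outcomes are month-to-month changes: "each Feedback Group participant will provide up to three change score outcomes (for month $i-1$ to month i for $i=2,3,4". They are compared between arms by GEE. "The analysis model will include a constant term and the group indicator". Neither the link nor the working correlation is named. The version without covariates is designated primary.
- **Second detectable effect.** For the same 30 per arm, ICC of 0.20 and three scores, "then the detectable standardized mean difference will be" 0.86.

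Section 12.6 expects at most 10% dropout, which neither calculation uses.

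**The concern.** The power statement counts change scores, but its SD and its worked example are both of levels. The model tests changes. A difference in the average monthly change is not the same quantity as a difference in mean adherence, so the 80% cannot be carried from one to the other without further inputs. Two different detectable effects for one design also sit a few paragraphs apart.

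This matters for two reasons. The plan relies on the 5.59-point figure when it calls the power adequate. The pilot is also meant to feed a larger trial: it "will provide preliminary estimates that can be used to inform future power calculations". If the reported coefficient is per monthly change but is later read as a gap in level, a month-4 gap is understated threefold.

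**Working it through.** **Inputs.** From Section 12.1: 30 per arm; SD 11.42; three changes per person; ICC 0.20, stated as an upper bound; multiplier 2.8. The significance level is not stated. Since 2.8 = 1.96 + 0.84, I take two-sided 5% and 80% power. From Section 12.6: 10% dropout, or 27 per arm. The documents do not give the SD of a monthly change or the correlation between monthly levels.

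**1. The plan's 5.59.** SE = 11.42 × √[(2/30) × (1 + 0.2 × 2)/3] = 2.014, and 2.8 × 2.014 = 5.64 points, or 0.494 SD. Rounding to 0.49 first gives 0.49 × 11.42 = 5.596. Power at 5.59 is Φ(5.59/2.014 − 1.96) = 79%. The figure is reproduced, with 11.42 used as if it were the SD of one change score.

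**2. What the planned GEE estimates.** The changes 1→2, 2→3 and 3→4 sum to month 4 minus month 1. With complete data, an identity link and independence or exchangeable working correlation, the arm coefficient is the between-arm difference in (month 4 − month 1)/3. Fitting the GEE to simulated data confirmed this to rounding error. With another working correlation or missed visits it is only approximate.

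**3. The two readings of 5.59.**
- As a difference in every monthly change: 3 × 5.59 = 16.8 points by month 4, so 80% becomes 96.8%, not 85.59%.
- As a level gap at month 4: the coefficient is 5.59/3 = 1.86.

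A third possibility is a linear rise whose average over months 2–4 is 5.59 (2.795, 5.59 and 8.385 points). Its coefficient is 8.385/3 = 2.80.

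**4. Why the stated inputs do not fix the power.** The variance of month 4 − month 1 needs either the SD of a change together with the correlation among changes, or the level SD together with the month 1–4 correlation r. The plan gives a level SD and a bound on the correlation among changes. Using 11.42 for changes as well, at ICC 0.20, gives SD(month 4 − month 1) = 11.42 × √(3 × 1.4) = 23.4. That exceeds 2 × 11.42 = 22.8, the maximum possible when levels have SD 11.42. The stated ICC therefore cannot stand in for the missing input.

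**5. Power over a range of r.** Assume a level SD of 11.42 and 30 per arm. SE of the arm difference in (month 4 − month 1) = 11.42 × √[2(1 − r)] × √(2/30).

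| r | 5.59 points at month 4 | Linear rise averaging 5.59 (8.385 at month 4) |
|---|---|---|
| 0.2 | 32% | 61% |
| 0.5 | 47% | 81% |
| 0.7 | 69% | 96% |
| 0.8 | 85% | 99% |

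For example, at r = 0.5 the SE is 11.42 × 0.258 = 2.95; 5.59/2.95 = 1.90, and Φ(1.90 − 1.96) = 47%. Reaching 80% needs r of about 0.77 for the month-4 gap and about 0.48 for the linear rise. With 27 per arm these become 0.79 and 0.54. Simulated GEE fits for a 5.59-point gap held from month 2 rejected in 34%, 50% and 85% of data sets at r = 0.2, 0.5 and 0.8, close to the formula's 32%, 47% and 85%.

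**6. The 0.86.** 2.8 × √[(2/30) × 1.4] = 0.855 SD, and 0.855 × 11.42 = 9.8 points. Dividing by the three scores inside the root gives 0.494 SD, or 5.64 points, as in step 1. By the undivided formula, 5.59 points has Φ(5.59/(11.42 × 0.3055) − 1.96) = 36% power. This conflict does not depend on r.

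**The case against.** The best defence is that the power sentence is built on the planned outcome. It counts change scores and bounds their ICC, and if 11.42 is read as the SD of a change, 5.59 is roughly what the GEE can detect per monthly change. That is a fair reading of the calculation, and it means the stated power cannot simply be called power for a level. It does not rescue the paragraph: the SD is reported as that of adherence itself, and the next sentence converts the 5.59 into 80% versus 85.59%.

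It is also fair that this is a pilot, that Wisepill openings are offered as an example, that the section warns only moderately large effects are detectable, and that changes are described as running from one month to the next. A later misreading of the coefficient is thus a risk, not a certainty. Against that, this is the only analysis specified, and the plan does claim adequate power.

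A reader might infer from the table that true power is 32% or 61%, by taking the plan's 0.20 as r. The documents do not support that, since both mentions of 0.20 concern change scores, not levels. A reader might also divide 1.86 by the SE of 2.014 and obtain 15%. That rests on the combination of inputs shown in step 4 to be impossible.

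**Conclusion.** The concern holds in two parts.

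- **The 80% is unsupported for the quantity tested.** The calculation joins a count and ICC of changes to an SD and an example of levels. No single reading gives both 5.59 points per change and 85.59% at month 4. For a 5.59-point gap at month 4, power is 32% to 85% over r = 0.2 to 0.8. This rests on a level SD of 11.42 taken from self-report (Wisepill may differ), complete data, an identity link, independence or exchangeable working correlation, and a two-sided 5% test.
- **The two detectable effects contradict each other.** 0.86 SD (9.8 points) and 5.59 points (0.49 SD) come from the same sample size, ICC and number of scores. The former leaves out the division by three.

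It would be tempting to conclude that the trial is underpowered or that 60 participants are too few. The documents do not show this. They give no value of r, and power passes 80% once r exceeds about 0.77 for a month-4 gap, or about 0.48 for the linear rise.

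**What to change.** Keep the change-score GEE and make the power statement refer to it.

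1. Estimate the SD of a monthly change and the correlation among changes from the Aim 1 repeated self-report data, if available (Section 5.1.4 describes 250 people with 12 monthly samples; Section 12.1 cites about 3,000 self-report observations). Otherwise show a range. Note that Wisepill may behave differently.
2. State one detectable difference and its power for the coefficient tested, allowing for the 10% dropout in Section 12.6. Replace both 5.59 and 0.86 with it.
3. Remove the 80% versus 85.59% illustration, or replace it with one that names the month and matches the tested quantity.
4. Name the link and the working correlation.
5. State that the reported effect is per monthly change, to be multiplied by 3 for the difference from month 1 to month 4.

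The cost is a recomputed power line and some wording, with no new visits or measurements. Analysing levels at months 2–4 adjusted for month 1 is an optional design choice, not part of this correction. It would also require amending the sentence that makes the unadjusted analysis primary.
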